### 12.3 Methods of Statistical Safety Analysis

The analysis of safety will be performed in the Safety Population.

AEs and concomitant diseases will be coded using the MedDRA coding dictionary.

Solicited AEs (reactogenicity):

Solicited local and systemic AEs gathered by the participants' diaries will be summarised for the 7-day period, by AE grading (mild, moderate, severe) and by treatment group. The number and percentage of participants with AEs will be presented. Fisher exact tests will be provided for a comparison of AE rates between treatment groups in summary tables.

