## 2.6 Inferential Analyses

The analysis for primary endpoint will compare adverse events rates up to day 56 between treatment groups using Fisher-Freeman-Halton test. The same overall test between treatment groups will be performed for all adverse event tables in the Day 56 analysis as well as the final analysis.

The immunogenicity analysis will compare the anti-zika-rsp VNT antibody geometric mean titer (GMT) in the Per Protocol (PP) analysis population between the treatment groups. GMTs and GMT ratios will be estimated by applying an analysis of variance including the factor treatment group. This will be done using log10 transformed data and taking the anti-log of the resulting point estimates for the least squares means, least squares means differences and the corresponding 2-sided 95% CIs.

P-values will also be provided to compare GMTs between the treatment groups adjusted for multiple comparisons according to Tukey-Kramer.

For the primary immunogenicity analysis, values below the lower limit of detection are replaced by half of the limit and values above the upper limit are replaced by the upper limit.

As sensitivity analysis, an analysis of immunogenicity will be applied, that does not use such imputation. Therefore, observations will be interval-censored and GMTs will be estimated by assuming normal distribution for the log-transformed values (intervals). Values below the lower limit of detection will be left-censored at the lower limit and values above the upper limit (if applicable) will be right-censored at the upper limit.

Seroconversion rates and positivity rates will be compared between groups using Fisher-Freeman-Halton test.

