### 6.2.2 *Derivations and Definitions*

- All solicited and unsolicited Adverse Events up to Day 56 (Visit 3) will be analyzed for the preliminary analysis and all AE in the database for the Final Analysis. The following rules will be applied to identify AEs up to Day 56 for preliminary analysis: In general, all AE with start date prior to or at Visit 3 are considered. If a subject has no Day 56 visit (Visit 3) then all AEs within 56 days from Visit 1 (Day 0) (Visit 1 + 56 days) are included. If start date of AE is incomplete (e.g. missing start day) and the AE could theoretically be within Visit 3, or if Visit 3 is not available, within 56 days from Visit 1 (Visit 1 + 56 days), it will be handled as AE up to Day 56 (Visit 3) and thus be included in the preliminary analysis. If start date of AE is unknown it will be handled as AE up to Day 56 visit (Visit 3) and thus be included in the preliminary analysis.
- Percentages for AE rates are based on N (treatment group totals).
- An Adverse Events is considered to be related to study treatment if “Relationship to Study Treatment” is answered with “definitely”, “probably” or “possibly” or the causality is missing.
- Tables showing “severe” events will include events with grade 3 or 4 or missing grade.
- In tables showing subjects with AEs by maximum severity, subjects will be counted only in the highest grading category (=“potentially life threatening”), but events will be counted in each reported grading category.

Adapted from:

STAT03\_A Statistical Analysis Plan

Version 6.0, Effective Date 16-Feb-2018

Confidential and intellectual property of Assign DMB. No part of this document or its contents may be duplicated, referenced, published or otherwise disclosed in any form or by any means without prior written consent of Assign DMB.

- In tables showing AEs by causality, subjects will be counted only in the strongest relationship category ("definitely"), but events will be counted in each category.

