| 1.4.1.6                           | 2.4.1.6  | Summary Table of unsolicited Adverse Events (Safety Population)   | 
 
• Any unsolicited AEs
 
• Any related unsolicited AEs
 
• Any severe unsolicited AEs
 
• Any serious unsolicited AEs
 
• Any medically attended unsolicited AEs
 
• Any related severe unsolicited AEs
 
• Any related serious unsolicited AEs
 
• Any related medically attended unsolicited AEs
 
• Any unsolicited AEs leading to second vaccination not administered
 
 |
| 1.4.1.7                           | 2.4.1.7  | Subjects with at least one Adverse Event classified by Maximum Severity (Safety Population)                   |  |
| Solicited Adverse Events   |          |   |  |
| 1.4.1.8                           | 2.4.1.8  | Subjects with solicited local Adverse Events by Symptom (Safety Population)                                   |  |
| 1.4.1.9                           | 2.4.1.9  | Subjects with solicited systemic Adverse Events by Symptom (Safety Population)                                |  |
| 1.4.1.10                          | 2.4.1.10 | Subjects with solicited Adverse Events classified by Maximum Severity (Safety Population)                     |  |
| 1.4.1.11                          | 2.4.1.11 | Subjects with solicited local Adverse Events by Symptom classified by Maximum Severity (Safety Population)    |  |
| 1.4.1.12                          | 2.4.1.12 | Subjects with solicited systemic Adverse Events by Symptom classified by Maximum Severity (Safety Population) |  |
| Unsolicited Adverse Events |          |   |  |
| 1.4.1.13                          | 2.4.1.13 | Subjects with unsolicited Adverse Events by PT (Safety Population)  |  |
| 1.4.1.14                          | 2.4.1.14 | Subjects with unsolicited Adverse Events by SOC and PT (Safety Population)                                    |  |
| 1.4.1.15                          | 2.4.1.15 | Subjects with related unsolicited Adverse Events by SOC and PT (Safety Population)                            |  |
| 1.4.1.16                          | 2.4.1.16 | Subjects with severe unsolicited Adverse Events by SOC and PT (Safety Population)                             |  |

|  |          |   |  |
|--|----------|---|--|
| 1.4.1.17   | 2.4.1.17 | Subjects with serious unsolicited Adverse Events by SOC and PT (Safety Population)                              |  |

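### The adverse-event test also covers the worst-grade tables, where a single-grade row cannot be read as better or worse tolerability and no row tests moderate or worse

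*Combined protocol and SAP*

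**What the plan says.** SAP 2.6 plans to "compare adverse events rates up to day 56 between treatment groups using Fisher-Freeman-Halton test" and then extends this: "The same overall test between treatment groups will be performed for all adverse event tables in the Day 56 analysis" and likewise at the final analysis. No table is exempted.

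SAP 7.1 lists six maximum-severity tables: x.4.1.7, x.4.1.10, x.4.1.11, x.4.1.12, x.4.1.24 and x.4.1.25. The first is titled "Subjects with at least one Adverse Event classified by Maximum Severity (Safety Population"). It also lists three causality tables, x.4.1.26 to x.4.1.28.

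SAP 6.2.2 sets the counting rules:
- Severity: "In tables showing subjects with AEs by maximum severity, subjects will be counted only in the highest grading category". A parenthesis then names the top of the scale. I read the rule as each participant's own worst grade, as the table titles imply. Events, unlike participants, are counted in every grade.
- Causality: "In tables showing AEs by causality, subjects will be counted only in the strongest relationship category".
- Denominator: "Percentages for AE rates are based on N (treatment group totals").
- Tables of severe events take grade 3, grade 4 or missing grade.

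The summary tables x.4.1.2 to x.4.1.6 contain rows for any AE, any severe AE and any related AE. No table has a row for grade 2 or worse.

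**The concern.** In a worst-grade table the categories exclude one another. A participant who moves from mild to moderate leaves the mild row, and one who moves from moderate to severe leaves the moderate row. The null hypothesis for a single row is therefore an equal probability that the worst grade was exactly that grade. This is not a hypothesis about tolerability. A vaccine that makes reactions worse lowers its own mild row, and a small p-value there looks like an advantage.

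This matters because safety is the primary objective and the other severity rows may carry little information. In the earlier trial of a similar candidate (protocol 4.4.1), solicited and unsolicited AEs occurred in 100% and 87.5% of the placebo group. One participant had a severe solicited AE and five had severe unsolicited AEs. If this trial behaves alike, the any-AE row is near its ceiling and the severe row nearly empty. The boundary between mild and moderate then holds most of the severity information, and no planned test addresses it directly.

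**Working it through.** **Inputs.** Group sizes A 14, B 14, C 12, D (placebo) 8, from protocol 6.3. The test and its scope come from SAP 2.6, the counting rule and denominator from SAP 6.2.2. The documents give no alpha for AE tests and no sample-size calculation, so there is no plan figure to reproduce. I assume a two-sided level of 0.05. All severity profiles below are assumptions.

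**Test.** For a row with counts x_A to x_D and total m, the table probability is C(14,x_A)·C(14,x_B)·C(12,x_C)·C(8,x_D) / C(48,m). The exact p-value sums this over all tables with the same m that are no more probable than the observed one.

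**Worked example** (A, B, C, D): none 3, 3, 2, 1; mild 3, 3, 3, 7; moderate 4, 4, 4, 0; severe 4, 4, 3, 0.

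| Row | Vaccinees | Placebo | p |
|---|---|---|---|
| Any AE | 32/40 | 7/8 | 1.00 |
| Worst grade mild | 9/40 (22.5%) | 7/8 (87.5%) | 0.008 |
| Worst grade moderate | 12/40 | 0/8 | 0.35 |
| Worst grade severe | 11/40 | 0/8 | 0.43 |
| Moderate or worse (not planned) | 12 + 11 = 23/40 | 0/8 | 0.024 |

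Tested row by row, the only significant grade row says that vaccinees had fewer mild reactions. The cumulative row says that they had more reactions of moderate grade or worse. One test on the whole four-by-four table gives p of about 0.21 (60,000 permutations).

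When every participant has an AE, the mild row is the exact complement of the moderate-or-worse row and the two p-values coincide. With mild 4, 4, 4, 7, both are 0.030. The evidence is then in the table but under a label that points the wrong way.

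**Simulation** (exact four-arm row tests; profiles are none/mild/moderate/severe in percent; the three vaccine arms share one profile):

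| Placebo | Vaccine | Mild row significant, fewer in vaccinees | Moderate row significant | Moderate or worse significant | Gain, cumulative over moderate row |
|---|---|---|---|---|---|
| 10/60/25/5 | 10/45/33/12 | 7% | 5% | 8% | 3 points |
| 15/60/20/5 | 10/30/35/25 | 24% | 7% | 28% | 21 points |
| 10/65/20/5 | 10/20/40/30 | 55% | 11% | 49% | 38 points |
| 10/70/15/5 | 10/10/50/30 | 88% | 28% | 82% | 54 points |

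In the three large-shift rows, the mild row is the only significant grade row in about 18%, 41% and 54% of trials. With no shift it is significant in this direction in about 2%.

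**The case against.** **The SAP does not say that each grade row gets a p-value.** This stands. The Fisher-Freeman-Halton test can be run on a whole group-by-grade table, and then the misleading mild-row result cannot occur. For solicited AEs, protocol 12.3 says that "Fisher exact tests will be provided for a comparison of AE rates between treatment groups in summary tables", and SAP 7.1 uses the title Summary Table only for x.4.1.2 to x.4.1.6. Yet SAP 2.6 is broader, and a comparison of AE rates reads most naturally as row by row. A reader might infer that the SAP is certain to print misleading p-values; the text does not support that. It leaves the matter open, and the moderate-or-worse comparison is absent either way.

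**The large shifts are extreme.** This also stands. They put severe reactions at 25% to 30% in vaccinees. In the earlier trial at most 1 + 5 = 6 of 48 participants (12.5%) had any severe AE, all judged unlikely or not related. The small-shift row belongs in the range, and there the gain is about 3 points.

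**The test is valid and the table can be read by eye.** Largely true. With equal severity the row tests reject in about 2% to 5% of trials, so there is no inflated error rate. Counts share the group denominator, and any-AE and severe rows exist. But adding rows by eye supplies no p-value, and the plan calls for p-values.

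**The causality tables.** One might infer the same gap there. It does not exist: SAP 6.2.2 defines related as possibly or stronger (or missing), and the any-related rows are already planned in the summary tables.

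**A rank test instead.** One might infer that a test using the grade order would do better. Within the SAP's four-arm comparison this is not shown. A Kruskal-Wallis test gives about 23%, 36% and 63% in the three large-shift settings, below the cumulative row in each.

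**Conclusion.** The point holds as a matter of what the planned p-values mean, not as a false-positive problem or a threat to the any-AE comparison. Under row-wise testing, a significant mild row has no fixed direction of benefit or harm, and the moderate row loses those who became severe. Under whole-table testing, the grade order is ignored. Under both, moderate or worse goes untested.

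The practical size runs from slight to large. The chance of a significantly lower mild row in vaccinees is about 7% for a small shift and 24% to 88% for large ones. These figures rest on a level of 0.05, identical profiles in the three vaccine arms, row-wise testing and assumed severity distributions. I would make the change because it is cheap, not because a large effect is expected.

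**What to change.** In SAP 2.6 and 6.2.2:
1. Keep the worst-grade counts for display and state that single-grade rows carry no p-value.
2. Add a cumulative row for grade 2 or worse to the six maximum-severity tables.
3. Apply the existing four-arm exact test to the cumulative rows: any grade, grade 2 or worse, grade 3 or worse.
4. In the causality tables, leave the single-category rows descriptive and refer to the tested related rows in the summary tables.

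This also settles whether the test is per row or per table. The cost is SAP wording, a little programming, and a few extra derived rows and tests in an exploratory safety analysis. No new data are needed.

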## 6.3 Laboratory Parameters

Data from the early termination visit or unscheduled visits will be listed only and will not be shown in summary tables by time point. Laboratory data from scheduled visits (VS, Visit 2 and Visit 3) will be tabulated by time point. Specifications on TLFs are provided in Section 7:

For details on table and listing content, see Section 7.

### 6.3.1 *Data points*

- Hematology
  - Hemoglobin
  - Hematocrit
  - Erythrocytes
  - Leukocytes
  - Neutrophils
  - Lymphocytes
  - Monocytes
  - Eosinophils
  - Basophils
  - Platelets
- Clinical Chemistry
  - Creatinine
  - Potassium
  - Sodium
  - Calcium
  - Aspartate Aminotransferase
  - Alanine Aminotransferase
  - Alkaline Phosphatase
  - Bilirubin
- Coagulation
  - Prothrombin Time
  - Activated Partial Thromboplastin Time
  - Fibrinogen
- Urinalysis
  - Specific gravity
  - pH

- Leukocytes
- Nitrite
- Protein
- Glucose
- Ketone
- Urobilinogen
- Bilirubin
- Erythrocytes

The following parameters will be analyzed descriptively by time point:

- Absolute values (summary statistics for hematology, clinical chemistry and coagulation)
- Absolute change from baseline (Screening) (summary statistics for hematology, clinical chemistry and coagulation)
- Number of subjects with values above/below normal range (for hematology, clinical chemistry and coagulation)
- Urinalysis results (summary statistics for quantitative parameters, frequency statistics for qualitative parameters)

### 6.3.2 *Derivations and Definitions*

- No conversion of laboratory parameters will be performed. The parameters listed above will be tabulated and listed in the units reported by the study site.
- Absolute change from baseline will be calculated as difference from value of the current visit and baseline value (screening).

## 6.4 Other Safety Parameters

### 6.4.1 *Data points*

Data from the early termination visit or unscheduled visits will be listed only and will not be shown in summary tables by time point. The following vital sign parameters will be summarized descriptively:

- Diastolic blood pressure
- Systolic blood pressure
- Pulse rate
- Temperature

The following data will be listed only:

- Pregnancy test
- Local tolerability
- Local tolerability – post vaccination

- Symptom-directed physical examination
- System-based physical examination

For details on table and listing content, see Section 7.

## 7. LIST OF TABLES, DATA LISTINGS AND FIGURES

### 7.1 List of Tables

| No. for prel. Analysis  | No. for FA      | Legend   | Content  |
|---|-----------------|--|--|
| Overall Subject Information  |                 |  |  |
| 1.1.1.1   | 2.1.1.1         | Subject Overview (All subjects)  | 
 
• Randomized
 
• Safety Population
 
• mITT Population
 
• PP Population
 
• Number of subjects that received first vaccination
 
• Number of subjects that received second vaccination
 
• Number of subjects that missed any vaccination
 
 |
| 1.1.1.2   | 2.1.1.2         | Protocol Deviations by Deviation Type (All subjects)                                     | 
 
• Any major PD
 
• Any major PD by category
 
• Any minor PD
 
• Any minor PD by category
 
   |
| 1.1.1.3   | 2.1.1.3         | Number of Screening Failures and Reasons   | 
 
• Number of screening failures
 
• Reason for screening failure
 
   |
| 1.1.1.4   | 2.1.1.4         | Subjects by Visit (Safety Population)  |  |
| 1.1.1.5   | 2.1.1.5         | Study Status (Safety Population)   | 
 
• Visit attendance status
 
• Primary reason for early termination
 
  |
| 1.1.2.4-1.1.2.5   | 2.1.2.4-2.1.2.5 | Repeat tables x.1.1.4-x.1.1.5 for mITT population (if not the same as Safety Population) |  |
| 1.1.3.4-1.1.3.5   | 2.1.3.4-2.1.3.5 | Repeat tables x.1.1.4-x.1.1.5 for PP population  |  |
| NOTE: Overall Subject Information tables will also be provided for final analysis including all information reported during the study |                 |  |  |
| Baseline Evaluation  |                 |  |  |
| 1.2.1.1   | n/a             | Summary Table of Demographic Information (Safety Population)                             | 
 
• Age
 
• Gender
 
• Race
 
• Height [cm]
 
• Weight [kg]
 
  |
| 1.2.1.2   | n/a             | Vaccination History by and ATC Level 3 (Safety Population)                               |  |
| 1.2.1.3   | n/a             | Medical History Entry by SOC and PT (Safety Population)                                  |  |
| 1.2.1.4   | 2.2.1.4         | Prior Medications by ATC Level 2 and 3 (Safety Population)                               |  |
| 1.2.1.5   | 2.2.1.5         | Concomitant Medications by ATC Level 2 and 3 (Safety Population)                         |  |
| 1.2.1.6   | n/a             | Vital Signs at Baseline (Safety Population)  | 
 
• Systolic blood pressure [mmHg]
 
• Diastolic blood pressure [mmHg]
 
• Pulse rate [beats/min]
 
  |

Adapted from:

Page 23 of 33

STAT03\_A Statistical Analysis Plan

Version 6.0, Effective Date 16-Feb-2018

Confidential and intellectual property of Assign DMB. No part of this document or its contents may be duplicated, referenced, published or otherwise disclosed in any form or by any means without prior written consent of Assign DMB.

|  |                 |  |   |
|--|-----------------|--|---|
|  |                 |  | 
 
• Temperature [C]
 
 |
| 1.2.2.1-1.2.2.6  | 2.2.2.4-2.2.2.5 | For preliminary analysis repeat tables 1.2.1.1-1.2.1.6 and for final analysis tables 2.2.1.4-2.2.1.5 for mITT population (if not the same as Safety Population). |   |
| NOTE: Prior/Concomitant Medication tables will also be provided for final analysis but including all Prior/Concomitant Medications reported during the study |                 |  |   |
| Immunogenicity Analysis   |                 |  |   |
| Zika-RSP VNT Antibody   |                 |  |   |
| n/a  | 2.3.1.1         | GMT of Zika-RSP VNT Antibody by Visit (mITT Population)  |   |
| n/a  | 2.3.1.2         | GMT of Zika-RSP VNT Antibody based on interval-censored data by Visit (mITT Population)  |   |
| n/a  | 2.3.1.3         | ANOVA for GMT of Zika-RSP VNT Antibody between treatment groups by Visit (mITT Population)   |   |
| n/a  | 2.3.1.4         | Seroconversion rate for of Zika-RSP VNT Antibody by Visit (mITT Population)  |   |
| n/a  | 2.3.1.5         | Positivity of Zika-RSP VNT Antibody by time point  |   |
| Zika-RSP ELISA Antibody   |                 |  |   |
| n/a  | 2.3.1.6         | GMT of Zika-RSP-ELISA Antibodies by Visit (mITT Population)  |   |
| n/a  | 2.3.1.7         | GMT of Zika-RSP-ELISA Antibodies based on interval-censored data by Visit (mITT Population)  |   |
| n/a  | 2.3.1.8         | ANOVA for GMT of Zika-RSP-ELISA Antibodies between treatment groups by Visit (mITT Population)   |   |
| n/a  | 2.3.1.9         | Seroconversion rate of Zika-RSP-ELISA Antibodies by Visit (mITT Population)  |   |
| n/a  | 2.3.1.10        | Positivity of Zika-RSP-ELISA Antibodies by time point  |   |
| Measles-ELISA antibodies  |                 |  |   |
| n/a  | 2.3.1.11        | GMT of Measles-ELISA Antibodies by Visit (mITT Population)   |   |
| n/a  | 2.3.1.12        | GMT of Measles-ELISA Antibodies based on interval-censored data by Visit (mITT Population)   |   |
| n/a  | 2.3.1.13        | ANOVA for GMT Measles-ELISA Antibodies between treatment groups by Visit (mITT Population)   |   |
| n/a  | 2.3.1.14        | Seroconversion rate of Measles-ELISA Antibodies by Visit (mITT Population)   |   |
| n/a  | 2.3.1.15        | Positivity of Measles-ELISA Antibodies by time point   |   |

| T cell immunity    |                  |   |  |
|---------------------------|------------------|---|--|
| n/a                       | 2.3.1.16         | Median of SFC of T cell immunity-PBMCs by Visit (mITT Population)             |  |
| n/a                       | 2.3.1.17         | Positivity of SFC of T cell immunity-PBMCs by time point                      |  |
| n/a                       | 2.3.2.1-2.3.2.17 | Repeat Immunogenicity tables 2.3.1.1-2.3.1.17 for PP Population.              |  |
| Safety Results     |                  |   |  |
| Extent of Exposure |                  |   |  |
| 1.4.1.1                   | 2.4.1.1          | Extent of Exposure (Safety Population)  | 
 
• Study duration
 
• Treatment duration
 
   |
| Adverse Events     |                  |   |  |
| 1.4.1.2                   | 2.4.1.2          | Summary Table of solicited and unsolicited Adverse Events (Safety Population) | 
Number of subjects with:
 
 
• Any AEs
 
• Any related AEs
 
• Any severe AEs
 
• Any related severe AEs
 
• Any SAEs
 
• Any related SAEs
 
• Any medically attended AEs
 
• Any related medically attended AEs
 
• Any AEs leading to second vaccination not administered
 
   |
| 1.4.1.3                   | 2.4.1.3          | Summary Table of solicited Adverse Events (Safety Population)                 | 
 
• Any solicited AEs
 
• Any related solicited AEs
 
• Any severe solicited AEs
 
• Any related severe solicited AEs
 
• Any solicited SAEs
 
• Any related solicited SAEs
 
• Any medically attended solicited AEs
 
• Any related medically attended solicited AEs
 
• Any solicited AEs leading to second vaccination not administered
 
   |
| 1.4.1.4                   | 2.4.1.4          | Summary Table of solicited local Adverse Events (Safety Population)           | 
 
• Any solicited local AEs
 
• Any related solicited local AEs
 
• Any severe solicited local AEs
 
• Any related severe solicited local AEs
 
• Any solicited local SAEs
 
• Any related solicited local SAEs
 
• Any medically attended solicited local AEs
 
• Any related medically attended solicited local AEs
 
• Any solicited local AEs leading to second vaccination not administered
 
 |
| 1.4.1.5                   | 2.4.1.5          | Summary Table of solicited systemic Adverse Events (Safety Population)        | 
 
• Any solicited systemic AEs
 
• Any related solicited AEs
 
• Any severe solicited AEs
 
• Any related severe solicited systemic AEs
 
   |

|                                   |          |   |  |
|-----------------------------------|----------|---|--|
|                                   |          |   | 
 
• Any solicited systemic SAEs
 
• Any related solicited systemic SAEs
 
• Any medically attended solicited systemic AEs
 
• Any related medically attended solicited systemic AEs
 
• Any solicited systemic AEs leading to second vaccination not administered
 
  |
| 1.4.1.6                           | 2.4.1.6  | Summary Table of unsolicited Adverse Events (Safety Population)   | 
 
• Any unsolicited AEs
 
• Any related unsolicited AEs
 
• Any severe unsolicited AEs
 
• Any serious unsolicited AEs
 
• Any medically attended unsolicited AEs
 
• Any related severe unsolicited AEs
 
• Any related serious unsolicited AEs
 
• Any related medically attended unsolicited AEs
 
• Any unsolicited AEs leading to second vaccination not administered
 
 |
| 1.4.1.7                           | 2.4.1.7  | Subjects with at least one Adverse Event classified by Maximum Severity (Safety Population)                   |  |
| Solicited Adverse Events   |          |   |  |
| 1.4.1.8                           | 2.4.1.8  | Subjects with solicited local Adverse Events by Symptom (Safety Population)                                   |  |
| 1.4.1.9                           | 2.4.1.9  | Subjects with solicited systemic Adverse Events by Symptom (Safety Population)                                |  |
| 1.4.1.10                          | 2.4.1.10 | Subjects with solicited Adverse Events classified by Maximum Severity (Safety Population)                     |  |
| 1.4.1.11                          | 2.4.1.11 | Subjects with solicited local Adverse Events by Symptom classified by Maximum Severity (Safety Population)    |  |
| 1.4.1.12                          | 2.4.1.12 | Subjects with solicited systemic Adverse Events by Symptom classified by Maximum Severity (Safety Population) |  |
| Unsolicited Adverse Events |          |   |  |
| 1.4.1.13                          | 2.4.1.13 | Subjects with unsolicited Adverse Events by PT (Safety Population)  |  |
| 1.4.1.14                          | 2.4.1.14 | Subjects with unsolicited Adverse Events by SOC and PT (Safety Population)                                    |  |
| 1.4.1.15                          | 2.4.1.15 | Subjects with related unsolicited Adverse Events by SOC and PT (Safety Population)                            |  |
| 1.4.1.16                          | 2.4.1.16 | Subjects with severe unsolicited Adverse Events by SOC and PT (Safety Population)                             |  |

|  |          |   |  |
|--|----------|---|--|
| 1.4.1.17   | 2.4.1.17 | Subjects with serious unsolicited Adverse Events by SOC and PT (Safety Population)                              |  |
| 1.4.1.18   | 2.4.1.18 | Subjects with medically attended unsolicited Adverse Events by SOC and PT (Safety Population)                   |  |
| 1.4.1.19   | 2.4.1.19 | Subjects with related severe unsolicited Adverse Events by SOC and PT (Safety Population)                       |  |
| 1.4.1.20   | 2.4.1.20 | Subjects with related serious unsolicited Adverse Events by SOC and PT (Safety Population)                      |  |
| 1.4.1.21   | 2.4.1.21 | Subjects with related medically attended unsolicited Adverse Events by SOC and PT (Safety Population)           |  |
| 1.4.1.22   | 2.4.1.22 | Subjects with unsolicited Adverse Events leading to second Vaccination not administered (Safety Population)     |  |
| 1.4.1.23   | 2.4.1.23 | Subjects with unsolicited Adverse Events caused study discontinuation (Safety Population)                       |  |
| 1.4.1.24   | 2.4.1.24 | Subjects with at least one unsolicited Adverse Event by Maximum Severity (Safety Population)                    |  |
| 1.4.1.25   | 2.4.1.25 | Subjects with at least one medically attended unsolicited Adverse Event by Maximum Severity (Safety Population) |  |
| 1.4.1.26   | 2.4.1.26 | Subjects with at least one unsolicited Adverse Event by Causality (Safety Population)                           |  |
| 1.4.1.27   | 2.4.1.27 | Subjects with at least one medically attended unsolicited Adverse Event by Causality (Safety Population)        |  |
| 1.4.1.28   | 2.4.1.28 | Subjects with at least one serious unsolicited Adverse Event by Causality (Safety Population)                   |  |
| NOTE: Adverse Event tables will also be provided for final analysis but including all AEs reported during the study. For the preliminary analysis the wording "up to Day 56" and for the final analysis "up to study end" will be added in the title of AE Table x.4.1.2-x.4.1.28. |          |   |  |
| Laboratory Parameters   |          |   |  |
| 1.4.1.29   | n/a      | Absolute Values for Hematology Parameters by Parameter and Visit (Safety Population)                            |  |
| 1.4.1.30   | n/a      | Absolute Values for Clinical Chemistry Parameters by Parameter and Visit (Safety Population)                    |  |

|                                |     |   |  |
|--------------------------------|-----|---|--|
| 1.4.1.31                       | n/a | Absolute Values for Coagulation Parameters by Parameter and Visit (Safety Population)                       |  |
| 1.4.1.32                       | n/a | Absolute Changes from Baseline for Hematology Parameters by Parameter and Visit (Safety Population)         |  |
| 1.4.1.33                       | n/a | Absolute Changes from Baseline for Clinical Chemistry Parameters by Parameter and Visit (Safety Population) |  |
| 1.4.1.34                       | n/a | Absolute Changes from Baseline for Coagulation Parameters by Parameter and Visit (Safety Population)        |  |
| 1.4.1.35                       | n/a | Subjects with Hematology Parameters Outside Normal Range by Parameter and Visit (Safety Population)         |  |
| 1.4.1.36                       | n/a | Subjects with Clinical Chemistry Parameters Outside Normal Range by Parameter and Visit (Safety Population) |  |
| 1.4.1.37                       | n/a | Subjects with Coagulation Parameters Outside Normal Range by Parameter and Visit (Safety Population)        |  |
| 1.4.1.38                       | n/a | Urinalysis Results by Parameter and Visit (Safety Population)   |  |
| 1.4.1.39                       | n/a | Absolute Changes from Baseline for pH and Specific Gravity by Visit (Safety Population)                     |  |
| Other Safety Parameters |     |   |  |
| 1.4.1.40                       | n/a | Systolic Blood Pressure [mmHg] by Visit (Safety Population)   |  |
| 1.4.1.41                       | n/a | Diastolic Blood Pressure [mmHg] by Visit (Safety Population)  |  |
| 1.4.1.42                       | n/a | Pulse Rate [beats/min] by Visit (Safety Population)   |  |
| 1.4.1.43                       | n/a | Body Temperature [°C] by Visit (Safety Population)  |  |

